11.3 Response Criteria and Methods for Evaluation of Measurable Disease

PET-CT scans will be performed after Week 6 and Week 12 of nivolumab single agent therapy, and also after C2 of NIVO + ICE therapy. Once the PET-CT result is negative, it does not need to be performed again. Instead, a diagnostic quality CT of the neck, chest, abdomen, and pelvis will be performed. The determination of anti-tumor efficacy will be based on objective response assessments made according to the Lugano Criteria¹⁶ and treatment decisions by the investigator will be based on these assessments. Clinical response of progressive disease (PD), stable disease (SD), partial remission (PR), or complete remission (CR) will be determined at each assessment. CR will be defined as a Deauville Score of 3. Selection of up to 6 of the largest dominant nodes or nodal masses to follow for response assessment must be PET FDG-avid at baseline. Investigator evaluation of baseline radiographic assessment will enable study enrollment per inclusion criteria based on the presence of measurable disease $> 1.5 \text{ cm}$ evidenced by CT scan of the neck/neck/abdomen/pelvis or CT/PET scans. In addition, per the Lugano Criteria, these nodes or masses should be selected according to all of the following: They should be clearly measurable in at least 2 perpendicular dimensions; if possible, they should be from disparate regions of the body; and they should include mediastinal and retroperitoneal areas of disease whenever these sites are involved.

If the bone marrow was positive at baseline, a follow-up bone marrow aspirate and biopsy is required and must be negative for assessment of a CR. If the follow-up morphology is indeterminate, the biopsy tissue must be negative by immunohistochemistry or the patient will be assessed as a PR.

12 Statistical Considerations

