Original Cohort: The *primary study endpoint* is complete response (CR) rate at the time of AHCT and is based on the Lugano Criteria.¹⁶ The primary endpoint for the patient *safety monitoring* segment of the study is toxicity. Toxicity will be scored using the NCI CTCAE v4.03 Scale. Unacceptable toxicity in a given patient is defined as any non-hematologic or hematological grade 3/4 toxicity that does not resolve to a grade 1/2 within 14 days per NCI CTCAE v4.03 toxicity criteria and is considered at least possibly related to nivolumab and/or ICE, or any other regimen-related cause of death.

New Cohort (B): The first primary endpoint is unacceptable toxicity. Toxicity will be scored using the NCI CTCAE v4.03 Scale. Unacceptable toxicity in a given patient is defined as any non-hematologic or hematological grade 3/4 toxicity that does not resolve to a grade 1/2 within 14 days per NCI CTCAE v4.03 toxicity criteria and is considered at least possibly related to nivolumab and/or ICE, or any other regimen-related cause of death. **Updated Apr 27, 2021:** The phase 2 portion will evaluate the anti-lymphoma activity of the two-agent combination as assessed by CR rate using Lugano criteria, in patients with high-risk HL as the second primary endpoint.

Sample Size:

Original Cohort (A): Assuming 1) the nivolumab 240 mg flat dose and ICE doses are well tolerated and 2) the study does not close for futility, 43 evaluable (received at least one cycle of treatment) patients will be enrolled on the phase II portion of the study. Expected accrual for safety monitoring segment: n=6.

New Cohort (B): We plan to enroll and treat 18 eligible patients. With 18 patients, we can estimate the proportion of patients experiencing unacceptable adverse events with sufficient precision (standard error ≤ 0.12 , half width ≤ 0.23). **Expanded Sample Size (Anti-Lymphoma Activity):** The Cohort B phase 2

portion is expected to enroll and treat a minimum of 19 and a maximum of 35 patients at the Cohort B schedule.

Estimated Duration of the Study

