2.4 Overview of Proposed Study

This is an open label, multi-center phase II study of nivolumab as single agent and in combination with ICE chemotherapy in patients with relapsed/refractory Hodgkin lymphoma to induction chemotherapy. Nivolumab will be given 240 mg IV every 2 weeks in the nivolumab only stage for 12 weeks or 6 cycles.

Patients who only achieve stable disease after 6 weeks of single agent nivolumab can either receive an additional 6 weeks of single agent nivolumab, or receive a combination of nivolumab plus ICE for 6 weeks. The decision to go either way will be at the physician/investigator's discretion on a case-by-case basis. The rationale is that in patients with a radiographic response of SD who are clinically doing well, an immune response or tumor flares could be masking an actual PR or CR.

For those with progressive disease after 6 weeks/3 cycles, or those not in CR after 12 weeks/6 cycles, they will be given 240 mg IV every 3 weeks for 6 weeks or 2 cycles in the combination study with ICE. ICE will be given as per standard use. The primary efficacy endpoint of this study is complete response rate. Response will be assessed according to modified criteria for malignant lymphoma, based on Lugano criteria.¹⁶ Response assessment will be performed after 6 weeks of nivolumab alone, then after 12 weeks of nivolumab alone. In the NIVO + ICE stage, response assessment will be performed after 6 weeks. Patients who achieve a complete response (CR) after 12 weeks can go directly to AHCT. Patients who achieve a CR or PR to NIVO + ICE will go to AHCT.

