Because a number of patients are expected to be given ICE salvage therapy in combination with nivolumab, it will not be possible in these patients to isolate the treatment effect of nivolumab. Our clinical endpoint, however, is complete response rate at the time of transplantation. Our design is to assess 1) the toxicity of nivolumab + ICE chemotherapy and 2) the sequential approach of nivolumab alone, potentially followed by nivolumab + ICE, and the effect of this strategy on the CR rate at the time of transplant.

This study will be conducted in compliance with the protocol, Good Clinical Practice (GCP), and the applicable regulatory requirements.

2.5 Rationale for New Cohort (Cohort B).

With enrollment on the original design almost completed (Cohort A), we have found that 22 out of 28 patients responded to NIVO and have proceeded to AHCT without receiving the combination of NIVO+ICE. Thus we have not completely assessed the safety of NIVO+ICE, nor have we obtained a preliminary estimate of the anti-lymphoma activity of the combination, which was the primary objective for Cohort A. We therefore are unable to fully characterize the NIVO+ICE combination using the original trial design. An additional consequence of a large majority of patients achieving a complete response with

nivolumab alone and proceeding directly from NIVO to AHCT is that very few on-treatment biopsies have been obtained for the correlative studies that were designed to address the exploratory objectives. We propose to include a cohort of high-risk patients with relapsed or refractory HL after frontline therapy to receive a single dose of NIVO prior to NIVO+ICE combination. We have restricted this cohort to only include high-risk patients (e.g. primary refractory HL, extranodal disease at relapse) since these patients have the highest risk of treatment failure using salvage therapy and autologous stem cell transplantation and thus justify the use of combination therapy rather than a PET-adapted approach. In addition, patients who have received brentuximab vedotin as part of frontline therapy will be eligible since identification of a novel salvage regimen that does not contain brentuximab vedotin is an important unmet need in this population. On treatment biopsies will be obtained on all these patients after the single dose NIVO and prior to the first dose of NIVO+ICE.

Updated Apr 27, 2021

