^f PET-CT scans will be performed at end of weeks 6, 12, and 18. Once PET-CT is negative, it does not need to be performed again. Instead, a diagnostic quality CT of the neck, chest, abdomen, and pelvis will be performed.

^g Each subject will have either a fresh core or excisional biopsy of a tumor lesion prior to starting study therapy or will have available archival tissue from a biopsy that was performed after induction therapy.

^h Tumor biopsy (if safe and accessible) must be performed after the first CT/PET response assessment (and only in patients who did not reach CR). For patients (with PR) who are going to a second 6-week treatment with single-agent NIVO, biopsy may be performed at any time after the first CT/PET scan (but before any NIVO+ICE treatment). For patients (with SD or PD at first CT/PET) who are instead going to a 6-week treatment with NIVO+ICE, biopsy must be performed before starting NIVO+ICE.

ⁱ If feasible, all subjects will undergo biopsy of tumor lesion at the time of disease progression or relapse.

^j On Day 1 of Wks 1, 3, 5 of nivolumab, on Day 1 of Wks 1 and 4 of NIVO + ICE, and on last day of Wk 6 (C2D21) of NIVO + ICE or any day post-C2D21, but must be prior to AHCT.

^k Tumor measurements will be performed at the same time points indicated for PET-CT scans in footnote f.

^l Includes all patients, regardless of reason for end of protocol therapy; refer to [Section 5.5](#) for follow-up.

^m For patients who receive AHCT

ⁿ Refer to [Section 5.5](#) for post-AHCT survival assessments.

*Serum chemistry includes comprehensive metabolic profile: sodium, potassium, chloride, carbon dioxide, glucose, blood urea nitrogen, creatinine, AST, ALT, Alkaline phosphate, total bilirubin, calcium, albumin, total protein, magnesium, phosphate

** Women of childbearing potential must have a negative serum or urine pregnancy test (minimum sensitivity 25 IU/L or equivalent units of HCG) within 24 hours prior to the start of nivolumab.

† Must be performed within 10 days of treatment initiation.

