12.4 Statistical Analysis Plan

In general, data will be summarized by using counts and percents for discrete parameters, and by descriptive statistics (number of observations, mean, standard deviation, median, minimum and maximum) for continuous parameters. Response rates will be calculated as the percent of evaluable patients that have confirmed CR by radiographic response including CT and/or PET scans; 95% Clopper Pearson confidence limits will be calculated for this estimate. Toxicity information recorded will include the type, severity, and the probable association with the study regimen. Tables will be constructed to summarize the observed incidence by severity and type of toxicity. Baseline information (e.g., the extent of prior therapy) and demographic information will be presented as well to describe the patients treated in this study. Time to response and survival endpoints will be estimated using the product-limit method of Kaplan and Meier. The

cumulative incidence of relapse/progression and non-relapse mortality will be calculated as competing risks using the method of Gooley et al¹⁷.

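### Section 11.3 defines complete response by one Deauville score, with no range, and does not tie that score to the Lugano standard or to a negative PET-CT

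*Combined protocol and SAP*

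**What the plan says.** Section 11.3 is the only response-criteria section and makes no separate definition for either cohort. It bases the determination of efficacy, and the investigator's treatment decisions, on Lugano assessments. It then adds "CR will be defined as a Deauville Score of 3". No other place in the documents gives a Deauville rule.

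The same section says of follow-up imaging "Once the PET-CT result is negative, it does not need to be performed again", with diagnostic CT used instead. Footnote f of the study calendars (Sections 10.1 and 10.2) repeats this for both cohorts: "Once PET-CT is negative, it does not need to be performed again". Nowhere is a negative PET-CT expressed as a score.

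Elsewhere, CR is described as follows:

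- Protocol Synopsis, Endpoints, Cohort A: "complete response (CR) rate at the time of AHCT and is based on the Lugano Criteria".
- Protocol Synopsis, Endpoints, Cohort B: "as assessed by CR rate using Lugano criteria, in patients with high-risk HL as the second primary endpoint".
- Section 2.4: "Response will be assessed according to modified criteria for malignant lymphoma, based on Lugano criteria". The modification is not described.
- Section 11.1: response and stable-disease durations refer to the 2014 Lugano criteria.
- Section 12.4: the response rate is the "percent of evaluable patients that have confirmed CR by radiographic response including CT and/or PET scans", with no score given.

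**The concern.** A primary endpoint should be countable from its written definition. Here the one explicit definition names a single score. On the stated assumption that lower scores mean less uptake, a patient with a cleaner scan than a score of 3 would not be a CR under that sentence, yet presumably would have a negative PET-CT. An analyst who applies the sentence as written and one who applies the cited Lugano criteria could therefore count different patients.

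The imaging rule makes the gap harder to close later. Once a PET-CT is called negative, subsequent assessments may be CT only and yield no Deauville score, so the earlier PET-CT carries the last score that patient has.

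There is also a narrow effect on treatment. CR and PR follow the same path in Cohort A at week 6 (Sections 1 and 12.1.1) and after NIVO + ICE (Section 2.4). The CR call decides the path mainly at Cohort A week 12, where Section 12.1.1 sends patients in CR to transplant and the others to NIVO + ICE. For a patient already called PET-negative at week 6, the week 12 scan may be CT only.

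**Working it through.** **1. Do the designs that use the CR count reproduce?** Inputs are from Section 12.1.1. For a two-stage design with stage 1 size n1, stage 1 stopping bound r1, total n and final bound r:

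P(success | p) = Σ over x > r1 of Bin(x; n1, p) × P(Y > r − x), with Y ~ Bin(n − n1, p).

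| | n1, r1, n, r | p0, p1 | Type I error | Power |
|---|---|---|---|---|
| Cohort A | 15, 8, 43, 26 | 0.50, 0.70 | 0.0499 | 0.8044 |
| Cohort B | 19, 9, 35, 22 | 0.50, 0.74 | 0.0444 | 0.9004 |

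Both meet the stated targets (0.05 with 80%, and 0.05 with 90%). An exhaustive search returns exactly these designs as the optimal (A, totals 34 to 46) and minimax (B, totals 30 to 40) solutions. The sample-size arithmetic is sound; the difficulty is only in what is counted.

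**2. What does one change of status do to the estimate?** Cohort A: 1/43 = 0.023, or 2.3 points. Cohort B: 1/35 = 0.029, or 2.9 points. The documents give no distribution of Deauville scores, so the number of affected patients cannot be estimated.

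**3. Are the go/no-go decisions exposed on the reported data?** The remaining requirement is the final cut-off minus the CRs in hand. The rates tried are the design rate times 1.0, 0.9 and 0.8; the two reductions are assumptions used only to show a range.

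*Cohort A.* Section 2.5 reports that "22 out of 28 patients responded to NIVO and have proceeded to AHCT without receiving the combination of NIVO+ICE". Assume that these 22 are recorded CRs and that they stand. Then 27 − 22 = 5 more are needed among 43 − 28 = 15. If the 28 include the first 15 patients, stage 1 is also passed: the other 13 hold at most 13 of the 22, leaving at least 9, which is the number required.

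- P(X ≥ 5 of 15) = 0.999 at 0.70, 0.995 at 0.63, 0.979 at 0.56.

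*Cohort B.* Section 2.5 reports CR in all 13 patients treated so far. Assume that these stand. Stage 1 needs 10 and is already met. At the end, 23 − 13 = 10 more are needed among 35 − 13 = 22.

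- P(X ≥ 10 of 22) = 0.999 at 0.74, 0.988 at 0.666, 0.936 at 0.592.

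These probabilities take the recorded CRs as given. They do not test whether those CRs meet the written definition.

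**The case against.** The strongest reply is that Lugano plainly governs. The paragraph containing the sentence names it for both efficacy and treatment decisions, and the synopsis (endpoints and statistical considerations) and Section 11.1 repeat it. Section 2.4 carries the same citation, and Section 12.4 describes the imaging without setting a rival threshold. A reader might infer that the documents give no indication of which standard applies. They do not support that: Lugano is the named standard throughout. What survives is that an explicit definition sits beside it and is not aligned with it.

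A reader might also infer a proven conflict with Lugano. The documents print neither the Deauville scale nor the Lugano score categories, so they cannot show one.

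The literal reading is also implausible in practice: all 13 Cohort B patients reported as CR would have scored exactly 3. That suggests sites use a different rule, but it is inference. It does not show which rule, and it does not show that anyone was misclassified.

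Finally, a symbol may have been lost in PDF reading. Inequality signs survive in the same section (the 1.5 cm measurability limit), but other marks look misread: the CBC row carries a dagger in the Cohort A calendar and an f in the Cohort B one. The possibility stands, so the source file must be checked before the wording is treated as an error.

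**Conclusion.** The point holds as a defect of wording in a primary endpoint and should be fixed. It rests on two conditions: that no symbol was lost, and that scores below 3 mean less uptake. At risk are the CR estimate and its match to its written definition, by 2.3 or 2.9 points per patient, with the number of patients unknown.

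A reader might infer a serious loss of power. If 10% of intended complete responders scored below 3 and were not counted, the unconditional chance of success would fall from 80.4% to 49.5% in Cohort A and from 90.0% to 61.8% in Cohort B. The documents do not support that conclusion: the 10% is invented, nothing shows that the literal rule is being applied, and the calculation ignores the reported results. If the recorded CRs stand, neither decision is materially exposed, which is why this is not a must-fix item.

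**What to change.** Check the source file for a lost symbol. If the sentence stands as printed:

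- Amend Section 11.3 to state the full set of Deauville scores counted as CR.
- Reconcile that set with the cited Lugano criteria, including the unexplained modification in Section 2.4, and with the meaning of a negative PET-CT in Sections 10.1, 10.2 and 11.3, for both cohorts.
- Confirm that the CRs already recorded used that definition.

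Because CR also routes treatment at Cohort A week 12, the sponsor must reconcile these passages; no clinical rule is proposed here. The cost is one amended sentence with its cross-references, plus a check of the scores behind recorded CRs. No scans, patients, sample sizes or Simon cut-offs change.

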12.1 Study Design

12.1.1 Phase II

This multi-institution, single-arm, phase 2 trial is designed to evaluate the anti-lymphoma activity of the nivolumab \pm ICE chemotherapy salvage regimen, in patients with relapsed or primary refractory Hodgkin lymphoma (HL) post induction chemotherapy. Activity will be assessed by complete response (CR) rate prior to autologous hematopoietic cell transplantation.

Nivolumab has demonstrated durable responses exceeding 6 months as monotherapy and in combination with ipilimumab in several tumor types, including NSCLC, melanoma, RCC, and some lymphomas.³⁸⁻⁴³ A phase I trial with 23 heavily pretreated patients with HL (78% of whom relapsed after receipt of brentuximab vedotin) was performed and revealed an ORR of 87% (17% CR, 70% PR) and PFS rate of 86% at 24 weeks.⁷ An extended analysis with a median of 20 months revealed durable responses, as 35% of responders (7 out of 20) maintained a response for over 1.5 years.⁴⁶ A phase II trial was conducted in patients who relapsed post AHCT and brentuximab vedotin, reporting an ORR of 66% (IRRC assessed: 9% CR, 58% PR) after a median follow up of 8.9 months.⁸ On the basis of these data, nivolumab was granted accelerated FDA approval for patients who progressed after AHCT and brentuximab vedotin. ICE salvage chemotherapy was shown to yield an ORR of 88% (26% CR, 58% PR, 3% minor response).³ The only potentially curative therapy for relapsed/refractory HL is salvage combination chemotherapy followed by autologous hematopoietic cell transplantation (AHCT).² Because the overarching research goal of this trial is to increase the proportion of subjects in CR just prior to AHCT, we will target a CR rate of 60%.

Patients will receive nivolumab single agent for 6 weeks. (See **Section 5.1.5.** for treatment schedule.) For patients who achieved CR/PR, they will receive additional 6 more weeks of nivolumab. For patients who

are in CR at this time, they will go directly to AHCT. For patients not in CR after 12 weeks of nivolumab, they will receive NIVO + ICE (combination of nivolumab plus ICE) x 6 weeks. Patients who only achieve SD after 6 weeks of single agent nivolumab can either receive an additional 6 weeks of single agent nivolumab, or receive a combination of nivolumab plus ICE for 6 weeks. The decision to go either way will be at the physician/investigator's discretion on a case-by-case basis. The rationale is that in patients with a radiographic response of SD who are clinically doing well, an immune response or tumor flares could be masking an actual PR or CR. For patients who only achieve PD after 6 weeks of single agent nivolumab, they will directly move onto the NIVO + ICE portion.

Study Design Rationale: This multicenter, single-arm, phase II trial is designed to evaluate the anti-lymphoma activity of the NICE 2nd-line regimen, in patients with relapsed or primary refractory HL post induction therapy. Activity will be assessed by CR rate prior to AHCT. Recent studies evaluating NIVO, an anti-PD-1 monoclonal antibody show efficacy in relapsed/refractory HL. In a phase I trial, NIVO was shown to have an ORR of 87% with a CR rate of 17%⁷. This response rate was recently confirmed in a phase II trial¹¹, and the drug received accelerated FDA approval for HL after failure of AHCT and BV treatment. In the Moskowitz study of PET imaging normalization prior to AHCT, 60% of patients who received 2nd-line ICE or augmented ICE achieved CR prior to AHCT¹². The MSKCC trial, which used augmented ICE, accrued 46 patients in 2 years, of whom 44 proceeded to AHCT, with 34 in CR (74%)¹³. In our study of PET-adapted BV ± chemotherapy prior to AHCT, 65% of enrolled/treated patients attained a CR pre-transplant¹⁴. Based on these data, a CR rate of 70% prior to AHCT will be considered promising, qualifying the regimen worthy of further investigation.

Study Design Characteristics: This phase II trial will implement a Simon Two-Stage Optimal Design¹⁵ to evaluate the anti-lymphoma activity of NIVO± ICE chemotherapy. The trial is expected to enroll a minimum of 15 and a maximum of 43 subjects. The sample size is based on the desire to discriminate a promising CR rate of 70% from a disappointing CR rate of 50% (a rate below what can be achieved with ICE/augmented ICE) using a type I error rate of 0.05 and power of 80%. At stage 1, 15 subjects will be entered on the study. If ≤ 8 complete responses are seen, the study will be terminated. If at least 9 subjects achieve a CR, the trial will continue to the second stage. At stage 2, 28 additional subjects will be entered. At the end of stage 2, if 27 or more subjects experience a complete response, the combination will be considered worthy of further study. If ≤ 26 subjects experience a complete response then no further investigation of the regimen is warranted.

Safety Monitoring Segment: NIVO is already FDA approved for treatment of HL and thus does not require special safety monitoring. Since the combination of nivolumab and ICE has not been tested before, the trial will include a 6-patient safety monitoring cohort for patients treated with nivolumab plus ICE (cycle 1). If $\leq 1/6$ patients experience unacceptable toxicity, then the study will continue. If 2 or more patients experience unacceptable toxicity, we will stagger the dose of nivolumab and ICE by 1 week so that nivolumab will start on day 1 and ICE will start on day 8 of a 21 day cycle. There will then be another 6 patient cohort added to the monitoring. If $\leq 1/6$ patients experience unacceptable toxicity in the staggered cohort, then the study will continue. If, however, 2 or more patients experience unacceptable toxicity in the staggered cohort, then nivolumab will not be given in combination with ICE.

Cohort B: Due to the high CR rate with nivolumab alone, only a small number of patients have been treated with NIVO + ICE thus far. Based on the small number of patients treated with NIVO + ICE, it is not possible to adequately characterize the full spectrum of toxicities with NIVO + ICE, nor is it possible to obtain an adequate preliminary estimate of the anti-tumor efficacy. Therefore, a separate cohort has been added to the study, which will be enrolled after the completion of the original PET-adapted cohort. In this new cohort, all patients will receive a cycle of nivolumab and then NIVO + ICE x 2-3 cycles. We plan to enroll and treat 18 eligible patients in this new cohort. The sample size is based on assessing unacceptable toxicities with NIVO + ICE. With 18 patients, we can estimate the proportion of patients experiencing unacceptable adverse events with sufficient precision (standard error ≤ 0.12 , half width ≤ 0.23).

Updated April 27, 2021:

Given the exceptionally high CR rate observed thus far and without any signals of excess toxicity to date, we will expand Cohort B to a full Phase 2 efficacy cohort to assess whether the CR rate after 3-4 cycles of therapy (Nivolumab x 1, Nivolumab+ICE x 2-3) in high-risk patients is promising compared to historical data. See full rationale provided in Section 2.5.

The phase 2 portion will implement a Simon two-stage minimax design^{15,87} to evaluate the anti-lymphoma activity of the two-agent combination as assessed by CR rate, in patients with high-risk HL. The Cohort B phase 2 portion is expected to enroll and treat a minimum of 19 and a maximum of 35 patients at the Cohort B schedule. The sample size is based on the desire to discriminate a promising CR rate of 74% from a disappointing response rate of 50%³ using a type I error rate of 0.05 and power of 90%. At stage 1, 19 patients will be entered on the study. Note: The n=13 patients treated thus far as part of the safety evaluation portion of the study will count toward the 35 patients required; given this, we expect to enroll only 22 new patients on the Cohort B phase 2 trial. If ≤ 9 complete responses are seen, the study will be terminated. If at least 10 patients achieve CR, the trial will continue to the second stage. At stage 2, 16 additional patients will be entered. At the end of stage 2, if 23 or more patients experience complete response, the combination will be considered worthy of further study. If ≤ 22 patients achieve a complete response then no further investigation of the combination is warranted.

